### 3.2 EXCLUSION CRITERIA

Exclusion Criteria for this study should comply with the stated contraindications on package inserts of G7 Acetabular System, Exceed ABT Acetabular System, Ceramic on Ceramic bearing and Taperloc Complete Microplasty stem. These indications are stated below:

Absolute contraindications include: infection, sepsis, and osteomyelitis

Relative contraindications include:

- 1) uncooperative patient or patient with neurologic disorders who are incapable of following directions,
- 2) osteoporosis,
- 3) metabolic disorders which may impair bone formation,
- 4) osteomalacia,
- 5) distant foci of infections which may spread to the implant site,
- 6) rapid joint destruction, marked bone loss or bone resorption apparent on roentgenogram, and
- 7) vascular insufficiency, muscular atrophy, or neuromuscular disease.

## Clinical Research Protocol

### 3.3. SUBJECT WITHDRAWAL

It is recognized that the subject's participation in this trial is entirely voluntary, and that she/he may refuse to participate and may withdraw from participation at any time without jeopardy to any future medical care. It is also recognized that the investigator, at his/her discretion, may withdraw a subject from this study based upon his/her professional judgment. In event of subject withdrawal, applicable local procedures should be followed

### 3.4. Subject withdrawal

Subjects may be withdrawn from the trial at any time for any of the following reasons:

- At subject's own request
- Death of subject
- Failure to return for follow-up
- Removed from evaluation – a written explanation by the investigator is required.

#### 3.3.1 Early Termination of Clinical Investigation

The clinical investigation can be discontinued at the discretion of the Chief Investigator or of Sponsor in the case of any of the following:

- Inefficacy of the study device.
- Occurrence of adverse events unknown to date with respect to their nature, severity and duration or the occurrence of known adverse events with unexpected frequency.
- Acquisition of new scientific knowledge during the conduct of the study which shows that the sense or ethical claim of the study is no longer valid.

If the subject is withdrawn for any reason at any time a final evaluation form will be completed and the Sponsor will be notified.

## 4. PROTOCOL DEVIATION MANAGEMENT AND REPORTING

Protocol deviations are unplanned and unintentional events. Any changes in the research protocol during the period, for which IRB approval has already been given, may not be initiated without submission of an amendment for IRB review and approval.

Any protocol deviations occur during the trial will be reported to any necessary institutions to manage. And that information also is reported to IRB and Sponsor.

## 5. ADVERSE EVENT MANAGEMENT AND REPORTING

A record of all adverse events, including details of the nature, onset, duration, severity, relationship to the device, relationship to the operative procedure and outcome, will be made and provide to the Sponsor. The subject will be questioned about any adverse event(s) at each subsequent follow-up assessment visit. Serious Adverse Events that are related to the device should be reported to the Ethical Committee and Sponsor as soon as possible. These include any untoward medical occurrences that result in death, are life threatening, require in patient hospitalization, or prolongation of existing hospitalization, result in persistent or significant disability/incapacity, or resulted in a congenital anomaly/birth defect.

***“Any general adverse events that are not related to hip, will be reported once symptomatic diseases are administered and confirmed by other departments.”***

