## 1.4. PURPOSES

The purpose of the study is to evaluate the safety and effectiveness of patients who received G7 Acetabular system in conjunction with Ceramic on Ceramic articulation and Taperloc Complete Microplasty stem in primary total hip arthroplasty compared to patients who received the Exceed ABT Acetabular system with the same combination.

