### 2.5.2. ASSESSMENT TIMELINES/SCHEDULE

Clinical and Radiographic Exams						
Data Collection item	Pre-operative	Intra-operative	Immediate Post-operative	6 Months	1 Year	2 years
Demographic and Medical History	X					
Operative Record		X				
Clinical Evaluation – OHS, HHS	X			X	X	X
Radiographic assessment			X	X	X	X
Squeaking, Dislocation			X	X	X	X
Adverse events including revisions			As required			

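### Section 5 makes reporting of non-hip adverse events wait for another department's confirmation, which conflicts with its own promise of a record of all adverse events; serious events not related to the device have no stated reporting speed

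*Combined protocol and SAP*

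**What the plan says.** Section 5 contains four statements that bear on this point.

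- Scope: the sponsor is to receive "A record of all adverse events, including details of the nature, onset, duration, severity, relationship to the device, relationship to the operative procedure and outcome".
- Elicitation: "The subject will be questioned about any adverse event(s) at each subsequent follow-up assessment visit".
- Speed: "Serious Adverse Events that are related to the device should be reported to the Ethical Committee and Sponsor as soon as possible". No number of days is given.
- Non-hip events: general events not related to the hip "will be reported once symptomatic diseases are administered and confirmed by other departments".

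Elsewhere, Section 1.4 sets out to "evaluate the safety and effectiveness of patients who received G7 Acetabular system" against the Exceed ABT combination, and Section 2.1 lists adverse events among the data collected prospectively. The schedule in Section 2.5.2 has a row for "Adverse events including revisions" whose timing is simply as required. Section 3.3.1 lets the Chief Investigator or the sponsor discontinue the investigation if previously unknown adverse events occur, or if known ones occur more often than expected.

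**The concern.** The first and last of those statements in Section 5 give a site two different instructions for the same event. One tells it to record and send everything. The other ties the report of a non-hip event to something that happens in another department, with no time limit, no exception for serious events and no rule for an event that is never referred or confirmed.

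With up to 4 sites (Section 2.2), each could apply the sentence in its own way, and the adverse event record would then partly reflect referral practice. That matters because safety is part of the stated purpose, and because the early-termination criterion turns on the nature and frequency of adverse events. Frequency is hard to judge if some events are held back or arrive late.

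The speed rule raises a second, smaller question. The section records relationship to the device and relationship to the operation as separate items, but attaches urgency only to the first.

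**Working it through.** **The plan's own figure.** The only computed figure in the plan is the sample size in Section 6.1: two-sided alpha 0.05, beta 0.20, SD 12, difference 5.8. By the normal approximation, n = 2 × (1.960 + 0.842)² × 12² / 5.8² = 67.2, rounded up to 68 per group. The t-based calculation gives 68.2, with power 79.9% at 68. With 15% dropout, 68 / 0.85 = 80. The plan's 68 and 80 are reproduced, and nothing in this point changes them.

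**Section 5 applied to each kind of event.** The table compares what the statements require.

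| Event | All-events sentence | Last sentence, literal reading | Last sentence, timing-only reading |
|---|---|---|---|
| Non-hip, never confirmed elsewhere | Record and provide to sponsor | Condition never met; need not be reported | Stays in the record, but no date is set for sending it |
| Non-hip, confirmed elsewhere | Record and provide to sponsor | Reported after confirmation, no time limit | Same |
| Serious, non-hip, not device-related | Record and provide to sponsor | Waits for confirmation | Waits for confirmation |
| Serious, procedure-related, hip | Record and provide to sponsor | Does not apply | Does not apply; Section 5 states no speed |

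The conflict lies in the first three rows. The literal reading can lose the first kind of event. Both readings delay the second and third. The fourth row is the gap in the speed rule. It contradicts nothing, because recording an event and expediting it are separate duties.

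**Does another section resolve it?**

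- Section 2.5.2 gives only as-required timing.
- Section 9.1 has data monitored at least annually and as often as monthly, with adverse event reports as a possible occasion. Section 9.3 adds sponsor review of all adverse reactions. Neither sets a time for a site to report an event.
- Section 10.1 binds the investigator to regulatory and ethics committee requirements, ISO 14155 and GCP. Their content is not in the documents.
- Section 10.2 covers forwarding the sponsor's safety reports to the ethics committee, which is the opposite direction from a site's report to the sponsor.

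**How far does questioning at visits help?** Follow-up visits fall at 6 months, 1 year and 2 years. The longest nominal gap is 24 − 12 = 12 months. With the windows in Section 2.5.3 it can reach (24 + 3) − (12 − 2) = 17 months. Questioning at visits supports completeness, but it is not a timely route for serious events.

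**Size.** The documents give neither adverse event rates nor the share of non-hip events that other departments would confirm. The following illustration therefore rests wholly on assumed values. Let p be the true risk of a given non-hip event and f the fraction reported. The chance that at least one such event appears among 80 patients in an arm is 1 − (1 − p × f)^80.

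| p | f = 1 | f = 0.75 | f = 0.50 | f = 0.25 |
|---|---|---|---|---|
| 2% | 80% | 70% | 55% | 33% |
| 5% | 98% | 95% | 87% | 63% |

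For example, with p = 2% and f = 0.50, 1 − 0.99^80 = 0.55. Incomplete reporting matters most for uncommon events, which is where the criterion on previously unknown events applies.

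**The case against.** The strongest defence is that the last sentence only sets the time at which a non-hip diagnosis is reported. On that view the all-events record and the questioning at each visit stay in force and nothing is lost. The wording allows this: it says once, not only if, and the sense of administered is unclear. This stands as a possible reading, and it means that an undercount is a risk and not an established fact. It does not remove the delay, the missing time limit or the silence on serious non-hip events.

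A second defence is that Section 10.1 brings in ISO 14155, GCP and regulatory requirements, which may supply a reporting route for serious events. That too is fair. The documents therefore do not show that such events have no route at all, only that Section 5 states none. A site following Section 5 should not have to settle the conflict from outside sources.

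A third defence is that the safety-related outcomes actually listed in Section 6.3 (dislocation, squeaking, radiographic assessment and survivorship) concern the hip or implant, so the non-hip sentence does not reach them. This is correct and limits the consequence.

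A reader might also infer that the rule biases the comparison between arms, through different confirmation rates or through relatedness judgements by staff who know the device. The documents do not support this. The confirming party is another department, and nothing suggests that it would act differently by cup type. The documents do not say who judges relatedness. An adverse event comparison by arm is not among the analyses listed in Section 6.3.

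**Conclusion.** The last sentence of Section 5 conflicts with the all-events record promised in the same section, and no other section reconciles them. Delay in reporting non-hip events, serious ones included, follows on either reading. Loss of unconfirmed events follows only on the literal one. Limiting the as-soon-as-possible duty to device-related serious events is a gap beside this conflict and not part of it.

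The size of any undercount cannot be computed; the illustrated probabilities depend on assumed event risks and reporting fractions. No imbalance between arms is shown. A reader might infer that the ethics committee loses its basis for stopping the trial, but Section 3.3.1 gives that decision to the Chief Investigator or the sponsor, and it is their information that is affected. The consequence is confined to the completeness and timeliness of the safety record and to the use of the early-termination criterion. The primary endpoint and the sample size are untouched.

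**What to change.** Replace the last sentence of Section 5 with: *Every adverse event reported or elicited at a visit is recorded on the CRF and provided to the Sponsor whatever its relation to the hip; confirmation by another department is added as follow-up information.*

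Add a sentence stating that serious events, including procedure-related and non-hip ones, are reported to the sponsor without waiting for that confirmation. Relationship to the device and to the operation are already recorded separately, so no new field is needed for them.

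In Section 6.3, add a table of recorded adverse events by arm.

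The cost is some extra reporting work at the sites and one more table. No visit is added, since subjects are already questioned at each one.

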# Clinical Research Protocol

## 6. STATISTICAL ANALYSIS PLAN

### 6.1 SAMPLE SIZE CALCULATION

This is a multi-center, randomized controlled study to compare G7 Acetabular System /CoC articulation/Taperloc Complete Microplasty stem with Exceed ABT Acetabular System /CoC articulation/Taperloc Complete Microplasty stem. The primary endpoint is Harris Hip Score at 1 year postop. Study sample size is determined assuming the use of an independent, two-sided, two-sample pooled t-test for differences in mean Harris Hip Score.

Assumptions:

$\alpha = 0.05$	Probability of Type I Error
$\beta = 0.20$	Probability of Type II Error
$sd = 12$	Estimated standard deviation of the differences based on current Exceed ABT CoC study in Korea

Based on the assumptions above, a mean difference in Harris Hip Score of 5.8 points between groups can be detected with 68 cases in each group. If 15% dropout/lost to follow-up is assumed this will give n=80 in each group.

A total of 160 cases will be enrolled in the study.

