#### Randomization

In this study, patients will be randomized to G7 Acetabular System with CoC articulation and Taperloc Complete Microplasty stem or Exceed ABT Acetabular System with CoC articulation and Taperloc Complete Microplasty stem in 1:1 randomization scheme. The randomization will occur via a random number generator (manual or computer) by Sponsor using block randomization procedure (block size of 4). The doctor or other health care professional does not choose the participants for each group. For patients satisfying inclusion criteria, randomization will occur by retrieving the next randomly generated group assignment. Sites will control randomization assignment.

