### 6.3 DATA ANALYSES

The following analyses will be performed:

Primary endpoint is Harris Hip Score (HHS) at 1 year follow-up.

Secondary endpoints include

- Harris Hip Score at 2 years postop
- Oxford Hip Score at 6 months, 1 and 2 years postop
- Radiographic Assessment at Immediate post-op, 6 months, 1 and 2 years postop
- Incidence of squeaking at different follow-up visits
- Dislocation rate at different follow-up visits
- Survivorship

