# Clinical Research Protocol

## Primary and Secondary Endpoint Analysis

Analysis for primary and secondary endpoints will use patient population which consists of those cases with complete data for one or more of the primary and secondary endpoints. Analysis is based on intention to treat principle.

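### Section 6.3 names no method for the primary 1-year HHS comparison; a prespecified ANCOVA on the pre-operative score would close the gap and add precision if baseline predicts outcome

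*Combined protocol and SAP*

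**What the plan says.** Sections 2.4 and 6.3 make HHS at 1 year the primary endpoint. Section 6.1 sizes the trial with two-sided alpha 0.05, beta 0.20 and SD 12: "Study sample size is determined assuming the use of an independent, two-sided, two-sample pooled t-test for differences in mean Harris Hip Score". It describes the SD as "Estimated standard deviation of the differences based on current Exceed ABT CoC study in Korea". The result is 68 evaluable per group for a 5.8-point difference, raised to 80 per group for 15% dropout.

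Section 6.3 opens with "The following analyses will be performed", but what follows is a list of endpoints. Its subsection on the primary and secondary endpoints defines the population as "those cases with complete data for one or more of the primary and secondary endpoints" and adds "Analysis is based on intention to treat principle". No test, model, covariate, effect estimate or confidence interval is named for 1-year HHS there or elsewhere. Section 6.2 fills missing clinical scores by last observation carried forward (LOCF).

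In the schedule (section 2.5.2), the row "Clinical Evaluation – OHS, HHS" is marked pre-operatively and at 6 months, 1 year and 2 years. The Randomization text describes sponsor-generated blocks of four and says "Sites will control randomization assignment". It does not say whether the blocks run within site. Section 2.2 allows up to four sites.

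**The concern.** A method assumed for sizing is not a method specified for analysis. As written, a t-test on 1-year scores, a t-test on change from baseline and a baseline-adjusted model would all fit the plan, and each can give a different p-value from the same patients. Section 8.1 provides for a report after each follow-up period, so data will have been reviewed before the final analysis, and the choice should be fixed before then.

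The second matter is efficiency. Power for 5.8 points is almost exactly 80%, with no reserve. If patients with better hips before surgery also tend to score higher at 1 year, an unadjusted comparison leaves explainable variance in the error term, although the covariate is being collected anyway.

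**Working it through.** **Inputs.** From section 6.1: SD 12, difference 5.8, two-sided alpha 0.05, power 0.80, 68 evaluable per group, 15% dropout. From section 2.2: at most four sites. Assumed: r, the correlation of pre-operative with 1-year HHS, varied from 0 to 0.5 because the documents do not give it; and SD 12 read as the SD of the 1-year score.

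**The plan's own figure.** The normal formula gives n = 2 × (1.960 + 0.842)² × 12² / 5.8² = 67.2, so 68 per group. Then 68 / 0.85 = 80 per group, 160 in total. The noncentral t (134 df) gives 79.9% power at 68 per group, a detectable difference of 5.81 at 80% power, and a 95% CI half-width of 1.978 × 12 × √(2/68) = 4.07 points. The stated sizes reproduce.

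**Baseline-only ANCOVA.** Residual SD = 12 × √(1 − r²). The variance of the treatment contrast is multiplied by 1 + 1/132 for estimating the slope, and df = 133. At r = 0.3, for example, the residual SD is 11.45 and the standard error is 11.45 × √(2/68 × 1.0076) = 1.97.

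| r | Power for 5.8 points | Detectable difference (80% power) | t-test n per group with the same power |
|---|---|---|---|
| unadjusted | 79.9% | 5.81 | 68 |
| 0 | 79.6% | 5.83 | 67.5 |
| 0.1 | 80.0% | 5.80 | 68.2 |
| 0.2 | 81.2% | 5.71 | 70.3 |
| 0.3 | 83.2% | 5.56 | 74.1 |
| 0.4 | 86.0% | 5.34 | 80.2 |
| 0.5 | 89.6% | 5.05 | 89.7 |

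The worst case, r = 0, loses 79.9 − 79.6 = 0.3 points. Power equals that of the t-test at r = 0.087. At r = 0.5 the gain is 89.6 − 79.9 = 9.7 points, worth about 22 more evaluable patients per group (89.7 − 68).

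**Adding site (four sites, three more parameters, df = 130).** If blocks are within site, the variance factor is 1 + 1/129 and the power column is the same to 0.1 point (break-even r = 0.090). If allocation ignores site, the factor is about 1 + 4/129. With site explaining nothing, power for r = 0 to 0.5 is then 78.7, 79.1, 80.3, 82.3, 85.2 and 88.9%. That is up to 79.6 − 78.7 = 0.9 points below baseline-only ANCOVA, and break-even against the t-test is r = 0.175. The site term repays its cost once it lowers the residual variance by the ratio (1 + 1/132) / (1 + 4/129) = 0.977, that is, once site explains about 2.3% of it.

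**Limits of these figures.** They are for 68 observed 1-year scores per group, not for the data set after LOCF. They also do not apply if SD 12 is the SD of within-patient change. In that case, with equal variances at both visits (an assumption), the 1-year SD would be 12 / √(2(1 − r)): 8.94 at r = 0.1, 12.0 at r = 0.5 and 15.49 at r = 0.7. The unadjusted starting point would itself move with r.

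**The case against.** The strongest reply is that the sizing paragraph signals the intended test, that this test is valid, and that one sentence naming it in section 6.3 would settle prespecification. On that view ANCOVA is a preference of unknown benefit. Much of this stands. Naming the t-test would indeed close the prespecification gap, and since r is not given, no particular gain can be promised; below r of about 0.09 adjustment loses slightly. But the risks are unequal, at most about 0.3 points lost against several gained at moderate r, from data already scheduled. That is more than taste.

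Three stronger readings are tempting and not supported:

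- A reader might infer that the t-test or the sample size is wrong. Neither is: the test is valid and 68 and 80 reproduce.
- A reader might infer that ANCOVA will add power whatever happens. That depends on r.
- A reader might infer that a site term belongs in the model only if the blocks are within site. That assumes site explains no variance, about which the documents say nothing; above about 2.3% of residual variance a site term gains even without within-site blocks.

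It is also fair to say that naming a model does not by itself define the primary analysis. LOCF in section 6.2 and the complete-data population in section 6.3 leave open who is analysed.

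**Conclusion.** The concern holds as an unspecified primary method and a missed efficiency gain, not as an error. The omission stands whatever r is. The precision gain is conditional: negligible at r of 0.1 or less, about 3 points of power at 0.3 (83.2 − 79.9 = 3.3), and material from about 0.4 (6.1 points there). The sizes rest on SD 12 being the SD of the 1-year score, a true difference of 5.8 points, and 68 observed outcomes per group. Nothing in the documents shows that an analysis would be chosen after results are seen; the point is only that the text leaves room for it. The sponsor should make the change before outcome data are reviewed.

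**What to change.** - **Section 6.3, primary analysis:** the adjusted mean difference in 1-year HHS with 95% CI, from an ANCOVA on treatment and continuous pre-operative HHS. Keep the pooled t-test as a supporting analysis and the sample size at 160.
- **Secondary scores:** analyse 2-year HHS the same way, and OHS with pre-operative OHS as covariate.
- **Missing pre-operative score:** replace it by the mean pooled over both groups, because LOCF has no earlier value to carry.
- **Analysis set:** state which patients enter, reconciling LOCF in section 6.2 with the complete-data population in section 6.3.
- **Site:** state in the Randomization text whether the blocks of four are within site. If they are, include site in the model. If not, a site term is optional and should be decided before outcome data are seen.
- **Section 6.1:** state whether SD 12 is the SD of the 1-year score or of change.

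The cost is a few sentences and trivial programming, with no new data or visits. Statistically, baseline adjustment uses one degree of freedom and costs at most about 0.3 power points if baseline is uninformative. An optional site term without within-site blocks could cost up to about 1 point more if site explains nothing.
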